1.2. Statistical Methods and Analysis Plan

This section describes the planned statistical analyses in general terms. A complete description of the methodology will be specified in a statistical analysis plan (SAP). Any changes in the statistical methods described in this protocol that occur prior to database lock will be documented in the SAP and will not require a protocol amendment.

1.2.1. General

Statistical analyses will be performed using two-sided tests.

Data will be summarized by treatment group (and by visit when applicable), with respect to demographic and baseline characteristics, efficacy variables, and safety variables.

Summary statistics will include the mean, N, standard deviation, median, minimum, and maximum values for continuous variables, and frequencies and percentages for categorical variables.

For the analyses of change from baseline, only patients with a baseline and at least one (1) post-baseline measure will be included in the analysis. Unless otherwise specified, baseline is defined as the latest non-missing observation across all the visits in the screening phase, before the active study drug begins. Endpoint will be the latest non-missing observation across all the post-baseline visits in the evaluation phase.

Low enrolling sites will be pooled for analysis and the pooling algorithm will be determined prior to breaking the blind. The goal of pooling low enrolling sites is to have a sufficient number of patients per treatment group within a site for the analysis models and for the evaluation of the treatment-by-site interaction for the primary endpoint. Unless otherwise specified, the pooled sites will only be used in the analyses where the site has an effect. The actual sites rather than the pooled sites will be specified in the data listings.

Details of the model and the analyses will be specified in the SAP. All statistical analyses will be performed using SAS®, Version 9.1.3 or higher.

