- 8. Any medical procedure requiring general anesthetic within three months of the Baseline Visit or any procedure requiring sedation within one month of the baseline visit;
- 9. Current clinically significant cardiovascular, respiratory, neurologic, hepatic, hematopoietic, renal, gastrointestinal or metabolic dysfunction unless currently controlled and stable, including (but not limited to) the following:
 - a. Uncontrolled diabetes mellitus defined as HbA1c >7%;
 - b. Positive hepatitis C antibody test (anti-HCF);
 - c. Positive hepatitis B surface antigen (HBsAg);
- 10. History (including family history) or current evidence of congenital long QT syndrome or known acquired QT interval prolongation;
- 11. History of intolerance and/or hypersensitivity to medications similar to tradipitant and its accompanying excipients;
- 12. Indication of impaired liver function (values for AST, ALT, or bilirubin > 2 times the Upper Limit of Normal (ULN));
- 13. Has a creatinine level > 1.25x ULN
- 14. Anyone affiliated with the site or sponsor and/or anyone who may consent under duress;
- 15. Any other sound medical reason as determined by the Investigator including any condition which may lead to an unfavorable risk-benefit of study participation, may interfere with study compliance or may confound study results.

Investigational product, dosage and mode of administration:

A single oral capsule of tradipitant 85 mg or matching placebo will be orally administered twice daily for a total daily dose of 170 mg.

Duration of treatment (Randomization Phase): 8 weeks

Reference therapy, dosage and mode of administration:

Placebo capsules will be provided in size and appearance identical to those containing VLY-686 and will be administered orally.

Objectives:**Primary Objective:**

- To evaluate the efficacy of VLY-686 in reducing worst itch in patients with chronic pruritus in atopic dermatitis as measured by Worst Itch Numerical Rating Scale (WI-NRS) at Week 8.

Secondary Objectives:

- To evaluate the efficacy of VLY-686 in improving disease severity in patients with atopic dermatitis as measured by the validated Investigator Global Assessment scale for Atopic Dermatitis (vIGA-AD).
- To evaluate the efficacy of VLY-686 in improving disease severity in patients with atopic dermatitis as measured by the SCORing Atopic Dermatitis (SCORAD) index and Eczema Area and Severity Index (EASI).

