- To evaluate the proportion of patients with improvement of WI-NRS \geq 4-point reduction.
- To evaluate the proportion of patients with improvement on SCORAD index of at least 50%, 75% or 90% improvement.
- To evaluate the proportion of patients with improvement on the EASI of at least 50%, 75% or 90% improvement.
- To assess the efficacy of tradipitant on global measures of improvement as measured by Clinical Global Impression of Change (CGI-C) and Patient Global Impression of Change (PGI-C).
- To assess the efficacy of tradipitant on quality of life as measured by the Patient Oriented Eczema Measure (POEM), Dermatology Life Quality Index (DLQI), Healthly Days Core Module (4 questions) (HRQOL-4), Insomnia Symptom Questionnaire (ISQ) and Patient Benefit Index - Pruritus (PBI-P).
- To explore the safety and tolerability of multiple oral doses of VLY-686.

Pharmacogenomic Sub-Study:

- Identify genetic markers that correlate with response to tradipitant treatment.
- Identify genetic markers that correlate with adverse events that may occur upon treatment with tradipitant.
- To identify genetic markers that are associated with atopic dermatitis and/or pruritus and disorders/diseases associated with NK-1 receptors.
- To identify genetic markers that are associated in the metabolism, distribution, and/or excretion of tradipitant and its metabolites.

Overall Design:

This is multicenter, randomized, double-blind, placebo-controlled study to be conducted in the United States. Approximately Three Hundred and Fifty (350) patients diagnosed with atopic dermatitis, who satisfy the selection criteria for the study, will be randomized to receive either tradipitant 85 mg or matching placebo BID.

The study is divided into two phases: the pre-treatment phase and the evaluation phase. The pre-treatment phase includes a screening and a baseline visit where patients' eligibility for the study will be assessed. Washout of medications will occur during the screening phase.

The evaluation phase includes 8 weeks of randomized, double-blind, placebo-controlled treatment. In-clinic evaluations will occur at Screening, Baseline, and Weeks 2, 4, 6, and 8.

Criteria for evaluation:

Efficacy:

Efficacy assessments will include:

- Worst Itch Numerical Rating Scale (WI-NRS)
- SCORing Atopic Dermatitis (SCORAD) index
- Validated Investigator Global Assessment scale for Atopic Dermatitis (vIGA-AD)
- Eczema Area and Severity Index (EASI)

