Study medication dispensation ¹⁰		X	X	X	X	
Study medication collection & compliance			X	X	X	X
Daily diary distribution and instruction	X					
Patient daily diary review		X	X	X	X	X

1 within +/- 3 days

2 Informed Consent will be obtained prior to performance of any study procedure(s)

3 Adverse Event collection will begin at the time the ICF is signed

4 If V1 cytokine panel sample is missed, sample should be drawn at the next in-clinic visit.

5 Sample collected at V1. Sample collected at V6/EOS only if randomized under Protocol Amendment 1 and sample was not already collected at V2.

6 Body height will only be collected at screening (V1), body weight will be collected at visits 1, 2, and 6.

7 An abbreviated physical examination will be performed at V2 (Baseline) and post-baseline visits 3-5 ONLY if clinically indicated.

- 8 The Screening/Baseline C-SSRS will occur at V1 (Screening). The Since Last Visit C-SSRS will occur at all other visits.
- 9 At V2 (Baseline), the Patient Needs Questionnaire (PBI-P(PNQ)) will be administered. The Patient Benefits Questionnaire (PBI-P(PBQ)) will be administered at subsequent visits.
- 10 Patients will be instructed to take their first dose of study medication on the evening of Day 0.

ET = Early Termination; WOCBP = Women of Child-bearing Potential; ECG = electrocardiogram; C-SSRS = Columbia Suicide Severity Rating Scale; NRS = Numeric Rating Scale; VRS = Verbal Response Scale; HbA1c= Haemoglobin A1c or glycated haemoglobin; IgE= Immunoglobulin E

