1.3. Efficacy Data Analysis

1.3.1. Primary Outcome and Methodology

The primary efficacy outcome measure for the double-blind phase will be the mean change from baseline in worst itch score, as measured by the Numerical Rating Scale (NRS) at Week 8. The primary statistical method will be the mixed effect model repeat measurement (MMRM). A detailed description of the primary analysis model and the corresponding sensitivity analysis will be included in the SAP.

As stated previously, any changes in the statistical methods that occur prior to database lock will be documented in the SAP and will not require a protocol amendment.

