1.3.2. Secondary Efficacy Analysis

The secondary efficacy outcomes include:

- DDSS
- Itch questionnaires including diary WI-NRS, site WI-NRS and VRS
- Proportion of patients with improvement of WI-NRS \geq 4-point reduction;

- SCORAD;
- EASI;
- Proportion of patients with improvement on SCORAD index of at least 50%, 75% or 90% improvement.
- Proportion of patients with improvement on the EASI of at least 50%, 75% or 90% improvement.
- vIGA-AD;
- PGI-C;
- CGI-C;
- PBI-P;
- HRQOL-4;
- POEM;
- DLQI;
- ISQ;
- Pharmacokinetic-Pharmacodynamic correlation.

Continuous endpoints will be summarized and analyzed in a similar manner as the primary endpoint. Categorical endpoints will be analyzed by a Cochran–Mantel–Haenszel (CMH) test. Details of the analysis will be described in the SAP.

Time to event data will be analyzed using the Kaplan-Meier method, and the treatment group differences will be tested by the log-rank test. Details of the analysis will be described in the SAP.

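### Does the last-observation Endpoint definition leave the responder outcomes and early-termination data without a usable rule?

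*SAP*

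**What the plan says.** Section 1.2.1 of the SAP has one paragraph on change-from-baseline data. It opens with who is included: "For the analyses of change from baseline, only patients with a baseline and at least one (1) post-baseline measure will be included". It then defines baseline and closes with "Endpoint will be the latest non-missing observation across all the post-baseline visits in the evaluation phase". No analysis is named as using this *Endpoint*.

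The primary outcome does not depend on it. The protocol's primary objective is worst itch "as measured by Worst Itch Numerical Rating Scale (WI-NRS) at Week 8", and SAP section 1.3.1 gives the outcome as "mean change from baseline in worst itch score, as measured by the Numerical Rating Scale (NRS) at Week 8", analysed by MMRM. Section 1.3.2 has the continuous secondary outcomes follow the primary approach.

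The responder outcomes are stated more briefly. The protocol synopsis has, for example, "To evaluate the proportion of patients with improvement on the EASI of at least 50%, 75% or 90% improvement", and SAP section 1.3.2 has "Proportion of patients with improvement on the EASI of at least 50%, 75% or 90% improvement". Neither gives a visit or a rule for missing values. Section 1.3.2 assigns a CMH test to categorical outcomes and adds: "Details of the analysis will be described in the SAP". Sections 1.2, 1.2.1 and 1.3.1 contain similar deferrals, and section 1.2 says that it describes the analyses only in general terms.

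Table 1 of the protocol has one final column for Day 56 or ET ("ET = Early Termination"), with a window of 3 days either side of Day 56. It does not say to which analysis visit an early-termination assessment belongs.

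**The concern.** There are three loose ends. The defined *Endpoint* has no named use, so a programmer might apply it to the responder outcomes by default. For those outcomes, carrying the last value forward, using observed Week 8 values only, and counting missing patients as non-responders are all open readings. An early-termination assessment on, say, Day 20 could be filed under Week 8 because the schedule puts it in that column.

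The outcome is not trivial to the sponsor: section 1.1 quotes about 91% power for a response difference. The plan also expects drop-out, since section 1.2.3 tabulates and tests discontinuation by arm. If the rule were picked once the drop-out pattern by arm was known, the responder result could be steered. If early-termination values were analysed as Week 8, the primary comparison would be touched as well.

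**Working it through.** **1. The plan's own figures.** Section 1.1 gives 175 per arm, a difference of 1.2 with SD 3, and response of 35% v 53%.

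- t-test: noncentrality = 1.2 / (3 × √(2/175)) = 3.74 on 348 df. Power is 96.2% (stated: about 96%).
- Fisher's exact test, two-sided 5%, by full enumeration at 35% v 53%: power 90.7% (stated: about 91%).

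Both reproduce, and the concern disputes neither.

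**2. How far the responder result depends on the rule.** The documents give no drop-out rate, no time course and no definition of response in section 1.1. The following are therefore assumptions:

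- Response means an improvement of at least 4 points, and 35%/53% are Week 8 rates.
- Improvement is normal with SD 3.
- Mean improvement at Weeks 2/4/6/8 is 1.60/2.20/2.60/2.84 on placebo and 2.41/3.35/3.92/4.23 on active.
- Everyone has a Week 2 value. A fraction d then drops out before each later visit, unrelated to the score.

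The response rate at a visit is 1 − Φ((4 − mean)/3). This gives 21.2/27.4/32.0/35.0% on placebo and 29.8/41.4/48.9/53.0% on active. The share of patients whose last visit is Week 2, 4, 6 or 8 is d, (1−d)d, (1−d)²d and (1−d)³.

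Worked case, d = 3% placebo and 7% active:

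- Week 8 is reached by 0.97³ = 91.3% and 0.93³ = 80.4%, so n = 160 and 141.
- Last observation, placebo: 0.030×21.2 + 0.0291×27.4 + 0.0282×32.0 + 0.9127×35.0 = 34.3%.
- Last observation, active: 0.070×29.8 + 0.0651×41.4 + 0.0605×48.9 + 0.8044×53.0 = 50.4%. The difference is 16.1 points.
- Non-responder counting: 0.9127×35.0 = 31.9% and 0.8044×53.0 = 42.6%. The difference is 10.7 points.
- Observed Week 8 only: 18.0 points, with fewer patients.

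| Drop-out per visit, placebo/active | Last observation | Observed Week 8 | Non-responder | Spread |
|---|---|---|---|---|
| 3%/7% | 16.1 points, power 83.6% | 18.0, 88.0% | 10.7, 50.6% | 7.3 |
| 5%/5% | 17.3, 88.6% | 18.0, 86.9% | 15.4, 82.6% | 2.6 |
| 7%/3% | 18.5, 92.5% | 18.0, 87.9% | 20.2, 97.0% | 2.2 |

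A cruder check with equal missingness agrees. With 10% missing per arm, observed-case power is 87.5% and non-responder power 85.4%. With 20% missing they are 82.9% and 77.8%.

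**3. Early termination and the primary outcome.** Suppose, against anything written, that early-termination values were analysed as Week 8. Use the plan's 1.2-point gap (active means 2.30/3.20/3.75/4.04) and 3%/7%:

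- Active: 0.070×2.30 + 0.0651×3.20 + 0.0605×3.75 + 0.8044×4.04 = 3.85.
- Placebo: 0.030×1.60 + 0.0291×2.20 + 0.0282×2.60 + 0.9127×2.84 = 2.78.
- The difference is 1.07 instead of 1.20. Mixing visits raises the SD to about 3.02, and power is 90.9%.

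For 5%/5% and 7%/3% the differences are 1.16 and 1.26.

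**4. The text side by side.** The *Endpoint* sentence closes a paragraph about change from baseline, and no sentence extends it to responders. The inclusion rule there and the Intent-to-Treat definition in section 1.2.2 say who is analysed. They do not say how a missing response is classified. The Day 56 or ET heading lists which procedures are done at the last contact. The text is silent on these points, but no two sentences conflict.

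**The case for a change.** The strongest case for acting is that deferral explains the silence without showing that the matter is settled. A few sentences fixed before unblinding would cost almost nothing, and section 1.2.1 already asks for that discipline with site pooling. The choice of rule can matter in either direction. With no treatment effect and 35% response in both arms, non-responder counting under 3%/7% drop-out gives 31.9% v 28.2%, and the Fisher test rejects 9.8% of the time. Reversing the drop-out gives the same 9.8%, now in favour of active.

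The gaps in the text are real, and so is the arithmetic. The safeguards are also incomplete. Sections 1.2 and 1.3.1 require method changes before database lock to be recorded in the SAP, and section 1.7 requires deviations to be justified, but none of them supplies a rule.

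The step from there to a fault in the plan does not stand. A missing-data rule and a visit map are the kind of detail that the fuller SAP exists to hold, and that document is not among those reviewed. There is also no single right rule to put in place of a wrong one: the three trade power against assumptions about drop-outs differently. The trial is double-blind, so a rule written into the fuller SAP before unblinding is chosen without sight of the results by arm.

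**Conclusion.** No change to the plan. The responder outcomes lack a visit and a missing-data rule in this text because it is a general description that points to a fuller SAP. Analysts would ordinarily settle both there, together with the assignment of early-termination assessments. The *Endpoint* definition does no harm where it stands, and the Week 8 MMRM primary analysis is not shown to be affected.

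The spread across rules is 2 to 3 points on an 18-point difference when drop-out is equal or higher on placebo. It reaches 7.3 points, with power from 50.6% to 88.0%, only if the active arm loses more than twice as many patients as placebo (cumulatively 20% v 9%). These figures rest on assumed drop-out, time course and meaning of response, and on drop-out unrelated to the score. They show why the rule should be on paper before unblinding, but they do not show that it is missing. When the fuller SAP is to hand, check that it names the responder visit, one missing-data rule with a sensitivity analysis under another, and the visit assignment of early-termination data.

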1.2.2. Patient Populations for Analysis

The following analysis populations will be defined for this study:

Intent-to-Treat: will include any patient randomized into the study that receives a dose of study drug and that has completed at least one post-baseline efficacy measurement while on study medication;

Safety: Any patient randomized into the study that receives a dose of study drug;

Per-Protocol: Any patient who is randomized and receives the protocol required study drug exposure and required protocol processing.

Efficacy analyses will be performed on the Intent-to-Treat population and the Per-Protocol population. Safety summaries will be based on Safety set. Patient characteristics will be presented for all patients randomized.

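### The set labelled Intent-to-Treat is a modified ITT: it drops randomised patients on post-randomisation conditions, including any whose only outcome was observed off drug; the likely effect is small and the repair cheap

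*SAP*

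**What the plan says.** SAP section 1.2.2 limits the Intent-to-Treat set to a randomised patient who "receives a dose of study drug and that has completed at least one post-baseline efficacy measurement while on study medication". On the sets used, it says: "Efficacy analyses will be performed on the Intent-to-Treat population and the Per-Protocol population". Neither is called primary. The same section uses the full randomised set for description only: "Patient characteristics will be presented for all patients randomized".

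SAP section 1.2.1 sets a data requirement for change-from-baseline analyses: "only patients with a baseline and at least one (1) post-baseline measure will be included in the analysis". It adds: "Endpoint will be the latest non-missing observation across all the post-baseline visits in the evaluation phase". Neither sentence mentions being on drug.

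In Protocol Table 1 the last visit column is Day 56 or ET ("ET = Early Termination"), with the efficacy scales scheduled. SAP section 1.3.1 makes the change in worst itch at Week 8 the primary outcome, analysed by MMRM, and promises that "the corresponding sensitivity analysis will be included in the SAP". SAP section 1.3.2 lists "Itch questionnaires including diary WI-NRS, site WI-NRS and VRS" among the secondary efficacy outcomes.

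The supplied statistics text calls itself general and defers detail to a fuller SAP. Part of it was removed before review, so statements here about what is not specified apply to the supplied text only.

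**The concern.** A reader of a Phase III report will take Intent-to-Treat to mean everyone randomised. Here, being dosed and being measured on drug are both events after randomisation, and the second can depend on treatment. Early stopping for adverse events could be commoner on tradipitant, and stopping for lack of efficacy commoner on placebo. If exclusions differ by arm and excluded patients differ in outcome, the comparison is biased in a direction that cannot be known in advance.

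The on-drug condition also discards data. A patient who stops before any on-drug measurement and is then seen at an early-termination visit meets the data requirement in section 1.2.1, but never enters the set to which it applies. With no primary set named in the supplied text, a result that differs between Intent-to-Treat and Per-Protocol has no pre-stated reading.

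**Working it through.** **Inputs from the documents.** SAP section 1.1: difference 1.2 points, SD 3, 175 per arm, two-sided 5%; response rates 35% and 53%. No loss or exclusion rate is given.

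**Plan's own figures.** Noncentrality = 1.2 / (3·√(2/175)) = 3.74 on 348 df, power 96.2% (stated: about 96%). Exact Fisher power for 35% vs 53% is 90.7% (stated: about 91%). Both reproduce.

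**Who is excluded.**

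| Randomised patient | Meets 1.2.1 data requirement | In the 1.2.2 set |
|---|---|---|
| Dosed, measured on drug | yes | yes |
| Dosed, only post-baseline value is off drug | yes | **no** |
| Dosed, no post-baseline value | no | no |
| Never dosed | only if measured | no |

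The on-drug condition governs entry to the set. It does not remove later off-drug values of patients already in it.

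**Bias on the primary scale.** This is a t-test approximation to the MMRM with no true effect among all randomised. *Assumed*: fractions ea (active) and ep (placebo) are excluded, and excluded patients do d points worse than retained ones. The retained mean in an arm is then too favourable by d·e, so bias = d·(ea − ep). Type I error comes from the noncentral t with 175(1 − ea) and 175(1 − ep) patients.

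| ea / ep | Bias, d = 1 to 3 | Two-sided type I error | Falsely favouring drug (nominal 2.5%) |
|---|---|---|---|
| 1% / 0% | 0.01 to 0.03 | 5.0–5.1% | 2.7–3.1% |
| 2% / 0% | 0.02 to 0.06 | 5.0–5.4% | 2.9–3.8% |
| 5% / 0% | 0.05 to 0.15 | 5.3–7.5% | 3.5–6.7% |
| 6% / 3% | 0.03 to 0.09 | 5.1–5.9% | 3.1–4.6% |
| 3% / 6% | −0.03 to −0.09 | 5.1–5.9% | 2.0–1.3% |
| 3% / 3% | 0 | 5.0% | 2.5% |

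At 3%/6%, power for a true 1.2 points is 94.5–92.1%.

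**How much the on-drug condition itself contributes.** Let a fraction r of the excluded have an off-drug value, counted as their Week 8 outcome. Remaining bias = d·e·(1 − e)(1 − r) / (1 − e(1 − r)). For 5%/0%, r = 0.5 gives 0.024 (d = 1) to 0.073 (d = 3), and type I error falls from 5.3–7.5% to 5.1–5.6%. At r = 0 nothing changes. The supplied text does not map an early value to Week 8, so this gain is an upper bound.

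**Responder endpoints.** Unstratified CMH, exact enumeration, 35% true response in both arms.

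- *If excluded patients are all non-responders*, leaving them out of the denominator creates a spurious difference. At 5%/0%: 0.35·175/166 − 0.35 = 1.9 percentage points, type I error 6.1%. At 6%/3% (164 and 170 retained): 1.3 points, 5.5%.
- *If excluded patients respond like the rest*, counting them as non-responders creates one instead. At 3%/6%: 35% × (0.06 − 0.03) = 1.05 points, error 5.4%. At 0%/5%: 1.75 points, 6.3%.

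Neither convention is free of assumption.

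**The case against.** The strongest reply is that the affected group may be close to empty. Diary WI-NRS is listed as an efficacy outcome, the diary is daily, and dosing starts on the evening of Day 0. If one diary entry on drug qualifies, almost every dosed patient is in the set. Nor need an early-termination value be off drug: Table 1 collects medication at that visit, so some patients may still be taking it. This stands as a limit on size. The text does not say whether a diary entry counts, and the wording excludes off-drug-only patients wherever they occur.

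A reader might infer that sections 1.2.1 and 1.2.2 contradict each other. They do not: one defines a set, and the other states the data needed for one kind of analysis within it. The comparison shows only that the on-drug condition discards usable values.

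A reader might also infer that the set definition inflates type I error to 7.5%. The documents do not support that. The figure needs 5% loss in one arm, none in the other and a 3-point deficit, all assumed. A patient with no post-baseline value gives an MMRM almost no information whatever the set is called, so most of that error is missing-data bias.

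Finally, section 1.2.3 tabulates discontinuations by reason, visit and arm for all randomised patients, and section 1.3.1 promises a sensitivity analysis. Both help. Neither counts exclusions from the efficacy set, and the content of the sensitivity analysis is left open.

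**Conclusion.** The point holds as a matter of definition: the set is a modified ITT under an ITT label, and its on-drug condition excludes patients whose outcome was observed. That part is certain from the text. The size is not. It rests on assumed loss rates, assumed deficits and a t-test stand-in for the MMRM. It is probably small, with type I error of 5.0–5.4% at 1–2% one-sided loss and no bias when losses and deficits are equal. The direction could favour either arm. The lack of a named primary set is a gap in the supplied text, which the fuller SAP may close. Severity: minor to moderate.

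**What to change.** 1. In section 1.2.2, define ITT as all randomised patients analysed as randomised, and delete the closing on-medication condition. Name this set the primary efficacy population and Per-Protocol supportive.
2. Keep the present set as a labelled modified-ITT sensitivity analysis. State whether a diary WI-NRS entry qualifies, and report exclusions by arm.
3. Amend section 1.2.1 so that its post-baseline requirement does not block imputation.
4. Within the sensitivity analysis promised in section 1.3.1, impute patients with no post-baseline value under an unfavourable assumption, such as no change from baseline or a reference-based method.
5. For responder endpoints, use all randomised patients as denominator with non-response imputation as a stated assumption. Test it with at least one alternative, such as multiple imputation.

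**Cost.** Wording in two sections, a few extra runs and one table. Section 1.2 lets changes made before database lock go into the SAP without a protocol amendment. The estimate may shrink: if 5% or 10% of the active arm has no benefit, 1.2 becomes 0.95 × 1.2 = 1.14 or 0.90 × 1.2 = 1.08, with power 94.3% or 91.9% against 96.2%. For responders, if 53% and 35% describe retained patients only, non-response imputation moves CMH power from 92.4% to 91.0% (3%/3% loss, active/placebo), 85.3% (6%/3%) or 94.0% (3%/6%). If those rates already count drop-outs as non-responders, nothing is lost; section 1.1 does not say.
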